19. PREGNANCIES

To ensure patient safety, each pregnancy occurring while the patient is on study treatment must be reported to the Safety Responsible of the study within 24 hours of learning of its occurrence. Occurrence of Pregnancy should be monitored for 90 days after stopping treatment (i.e. End of treatment or Cross-Over End of treatment whichever comes last). The pregnancy should be followed up to determine outcome, including spontaneous or voluntary termination, details of the birth, and the presence or absence of any birth defects, congenital abnormalities, or maternal and/or newborn complications. The follow-up to three months after delivery is mandatory for all reported pregnancy cases and in cases of live birth, the follow-up on any development issues or abnormality that would not be seen at birth.

Pregnancy should be recorded on a Clinical Trial Pregnancy Form and reported by the investigator to the Safety Responsible of the study within 24 hours from its learning. Pregnancy follow-up should be recorded on the same form and should include an assessment of the possible relationship to the study treatment any pregnancy outcome. Any SAE experienced during pregnancy must be reported on the SAE Report Form.

Pregnancy outcomes must be collected for the female partners of any males who took study treatment. Consent to report information regarding these pregnancy outcomes should be obtained from the mother.

Pregnancy and its follow-up should be also reported to Novartis safety desk within 15 calendar days of awareness.

e-mail:[contact]

[contact]

20. STATISTICAL CONSIDERATIONS

20.1. Study design

One year low dose (3,5 mg/kg/day DFX-FCT) in patients at the beginning of their transfusion history. Dose activity will be monitored by regular NTBI /LPI suppression and by prevention of iron accumulation (hepatic iron concentration and other tissue and serologic parameters) comparing baseline versus end of study iron concentration.

[figure not shown]
A standard pre-transfusional hemoglobin level will be indicated (Hb threshold for transfusion Hb 9 g/dl or 10 g/dl for patients with cardiac disease) to be maintained during the study year. Pre transfusional hemoglobin level and transfusions date and frequencies will be recorded. A transfusional ratio will be determined: number of units received in a predetermined period/ mean pre-transfusional Hb level.

Open label, single arm, fixed dose phase II study.

20.2. Sample size calculation

Including 50 subjects in the study, we can reach almost 60% power to detect small effect size 0.30 (with p value of 0.05) whereas, we have almost 100% to detect moderate effect size of 0.50 (with p-value of 0.05). On the basis of previous experience, the low dosage, the early intervention and the FCT preparation a 20% drop out rate is expected (10 additional patients to be enrolled)

Methods:

The power test was performed by G power 3.1 software by using the t test Means: Difference between two dependent means (matched pairs).

As demonstrated by our sample size analyses, we have enough power to detect an effect size between 0.3 and 0.5 considering a potential error of 0.05, which is largely accepted from scientific community.

The effect size is calculated on a common scale by G-power program which allows to compare the effectiveness of different variables on the same outcome. In other words, quantifies the magnitude of the difference of a variable between two population groups.

To interpret the resulting number, most scientists use this general guide developed by Cohen:

- < 0.1 = trivial effect
- $0.1 - 0.3$ = small effect
- $0.3 - 0.5$ = moderate effect
- > 0.5 = large difference effect

20.3. Statistical method and data analyses.

Analysis population: the planned enrolment target is 50 patients (+ 20% drop out rate) for a total number of 60 patients.

Data from all centers participating in this study will be pooled for analyses.

Standard descriptive analyses will include:

- Frequencies and percentages for categorical data;
- n, mean, standard deviation, minimum, median, 25th and 75th percentiles and maximum for continuous data.

Whenever possible, the analysis will be performed by visit.

Analysis sets

Full Analysis Set (FAS): All enrolled patients.

Safety analysis set (SS): All enrolled patients who will have received at least one dose of study drug and have at least one post-baseline safety assessment. Note that an entry on the Adverse Event CRF of a statement that a patient had no adverse events constitutes a safety assessment.

Per Protocol analysis set (PP): All enrolled patients who will have received at least one dose of study drug without any major protocol violations and complete the treatment study phase or withdraw from the study due to unsatisfactory therapeutic effect.

Patient demographics/other baseline characteristics

Demographic and other baseline data (including disease characteristics and transfusion history, etc) will be summarized descriptively for the Safety analysis set by means of the statistics above mentioned. Summary tables will be provided about medical history coded by System Organ Class and Preferred Term of MedDRA dictionary.

Treatments (study treatment, concomitant therapies, compliance)

The descriptive analysis listed below will be reported for the safety analysis set.

Study drug

The duration of study drug exposure, as well as average prescribed doses, will be summarized. Any dose adjustments and reasons that led to the adjustments will be listed. The number and duration of dose interruptions will also be described.

Compliance

Compliance based on prescribed amount of study medication versus amount of medication taken based on dispensed and returned amount of study medication will be summarized.

Concomitant Therapies

Concomitant medications and significant non-drug therapies prior to and after the start of the study treatment will be coded by WHO Drug Reference List dictionary and frequencies will be calculated according to drug classes.

The primary objective is prevention of iron accumulation measured by (primary variable) Change of hepatic iron from baseline according to baseline hepatic iron level: Baseline versus end of study.

For patients with baseline LIC ≤ 5 mg/g dry weight (dw) ± 1.5 mg/g dw.

For patients with baseline LIC > 5 mg/g dw $\pm 20\%$ (by R2- MRI ; test performed in a 1.5 tesla MRI machine and analyzed following R2 method (75).

The corresponding secondary efficacy variable will be the absolute change in hepatic iron concentration EOS versus baseline.

Difference between baseline versus EOT will be measured as continuous variables and analyzed with parametric or non parametric statistical tests depending by normality of distribution.

Secondary endpoint:

Observational: demographics and other baseline characteristics will be study with descriptive statistics. Analysis will be done on FAS and PP.

As the same way secondary endpoints will be evaluated as continuous or nominal variables and analyzed accordingly with parametric or non parametric tests. Efficacy parameters analysis will be done on FAS and PP.

Final Safety parameters will be measured in full analyses set and in all patients who received at least one dose of study drug (safety set).

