Study design	
 • This is an open-label, single arm, phase II, study designed to look whether early intervention with low dose DFX improves clinical outcome of patients with MDS. • Efficacy of early - low dose DFX FCT to prevent iron accumulation regularly suppressing reactive oxygen species. • Safety of early low dose DFX FCT. • Exploratory: possibility to guide chelation therapy by NTBI/LPI. • One arm • Fixed dose • Blinding: Open • Structure: Single Group • Randomized: Non-randomized • A standard pre-transfusion Hemoglobin level will be indicated (Hb threshold for transfusion Hb 9 g/dl or 10 g/dl for patients with cardiac disease) to be maintained during the study year. Pre transfusion hemoglobin level and transfusions date and frequencies will be recorded. A transfusional ratio will be determined: number of units received in a predetermined period/ mean pre-transfusion Hb level 	
Duration of the study	Enrolment 1 year. Per protocol treatment: 1 year. Total duration 2 years	
Number of patients	60 (50 + 10 for 20% drop out rate)	
Population	Adult MDS patients (≥ 18 years). Very low, low and intermediate risk group by revised-IPSS. Regularly transfused patients with low PRBC transfusion burden (less than 2 units/months for 3 consecutive months) at beginning of their transfusion story (total number of PRBC units received 5-20). Patients should not meet the published criteria for transfusion dependency (2 PRBC units /month for three consecutive months).	
Inclusion criteria	
Study population:
 
 • Diagnosis: Adult Myelodysplastic Syndrome (≥ 18 years). • Revised IPSS: very low, low – intermediate. 	

	
 Having received 5-20 packed red blood cell units Serum ferritin ≥ 300 ng/ml Transferrin saturation $\geq 60\%$ Chelation naïve Capability to provide informed consent

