	
 • Hypersensitivity to the active substance or to any of the excipients. • Inability to provide a valid informed consent. 															
Study treatment and response criteria	DFX FCT 3.5 mg/kg. Response criteria: prevention of iron overload as measured by liver iron concentration (MRI).															
Assessments schedule	MONTHLY															
Centralized analyses	
  
 TEST	REQUIRED	QUANTITY	
   
 NTBI, LPI, Epcidine, MDA	YES see schedule	7	
 
 Serum transferrin receptor, GDF11 e 15, Erythroferrone.	YES see schedule	5	
 
 NGS (molecular tumor analysis)	YES see schedule	2	
 
 MRI liver scan	YES Baseline and EOS	2	
  
	TEST	REQUIRED	QUANTITY	NTBI, LPI, Epcidine, MDA	YES see schedule	7	Serum transferrin receptor, GDF11 e 15, Erythroferrone.	YES see schedule	5	NGS (molecular tumor analysis)	YES see schedule	2	MRI liver scan	YES Baseline and EOS	2
TEST	REQUIRED	QUANTITY														
NTBI, LPI, Epcidine, MDA	YES see schedule	7														
Serum transferrin receptor, GDF11 e 15, Erythroferrone.	YES see schedule	5														
NGS (molecular tumor analysis)	YES see schedule	2														
MRI liver scan	YES Baseline and EOS	2														
Statistical considerations	
t tests - Means: Difference between two dependent means (matched pairs) Tail(s) = Two. α err prob = 0.05
 
Effect size dz
 
 —♦— = 0.5 —○— = 0.3 
Including 50 subjects in the study, we can reach almost 60% power to detect small effect size 0.30 (with p-value of 0.05) whereas, we have almost 100% to detect moderate effect size of 0.50 (with p-value of 0.05). On the basis of previous experience, the low dosage, the early intervention and the FCT preparation a 20% drop out rate is expected (10 additional patients to be enrolled) Methods: The power test was performed by G power 3.1 software by using the t test Means: Difference between two dependent means (matched pairs). As demonstrated by our sample size analyses, we have enough power to detect an effect size between 0.3 and 0.5 considering a potential error of 0.05 which is largely accepted from scientific community.
															

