11.2. Number of patients

A total of 60 patients will be enrolled in the study: 50 +10 for a planned 20% drop out rate (drop out rate estimated on others DFX DT – MDS prospective studies).

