16.4. Early withdrawn (discontinuation from study treatment)

- Physical Examination;
- ECOG;
- Vital Signs;
- Clinical Laboratory Evaluations;
- Electrocardiograms;
- Peripheral blood / bone marrow immunophenotyping in case of suspicious leukemic dissemination;
- Any test needed if withdrawal is for toxic reason.

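### The stated power and drop-out allowance do not reproduce: 50 pairs give 54.8% and 93.4% power, and 60 enrolled with 20% drop-out leave 48 pairs, not 50

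*Combined protocol and SAP*

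**What the plan says.** The synopsis (Statistical considerations) gives the G*Power settings: "Difference between two dependent means (matched pairs) Tail(s) = Two", alpha 0.05, with curves for dz 0.5 and 0.3. Section 20.2 names the same test and reports two powers. The first is "Including 50 subjects in the study, we can reach almost 60% power to detect small effect size 0.30". The second is "we have almost 100% to detect moderate effect size of 0.50". Both places then conclude that "we have enough power to detect an effect size between 0.3 and 0.5".

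The enrolment figure appears in four places. The synopsis (Number of patients) has "60 (50 + 10 for 20% drop out rate". Section 11.2 has "A total of 60 patients will be enrolled in the study: 50 +10 for a planned 20% drop out rate" and says the rate comes from other prospective deferasirox studies in MDS. Section 20.2 adds 10 patients for an expected 20% drop-out. Section 20.3 has "the planned enrolment target is 50 patients (+ 20% drop out rate) for a total number of 60 patients".

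The power figures themselves stand only in the synopsis and section 20.2. Section 11.2 and section 20.3 carry only the 50 + 10 count.

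**The concern.** These are the only sample-size and power figures in the plan, and every input needed to recompute them is given. Three things look wrong.

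- **Power.** Both figures seem too high for 50 pairs.
- **Drop-out.** Ten is 20% of the 50 evaluable patients, whereas a drop-out rate normally applies to those enrolled.
- **Conclusion.** Power is called sufficient down to an effect size at which the plan itself reports less than 60%.

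An ethics committee, the data monitoring committee or a later reader would take from this that an effect of 0.3 is adequately covered. A non-significant change in liver iron could then be over-read as evidence that iron was held in balance, although the test would miss a true dz of 0.30 nearly half the time.

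**Working it through.** **Inputs**

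- Test: matched-pairs t test, two-sided, alpha 0.05 (synopsis; test also named in section 20.2).
- Effect sizes: dz = 0.30 and 0.50 (synopsis, section 20.2).
- Evaluable n = 50; drop-out 20%; enrolled 60 (synopsis, sections 11.2, 20.2 and 20.3).

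**Formula.** The test statistic follows a non-central t distribution with df = n − 1 and non-centrality λ = dz × √n. Power = P(|T| > t at 0.975 with n − 1 df).

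**Step 1: the plan's own case, n = 50.** df = 49, critical value 2.0096.

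- dz 0.30: λ = 0.30 × √50 = 2.121; power 0.5477. The plan says just under 60%; the gap to 60% is 5.2 points.
- dz 0.50: λ = 0.50 × √50 = 3.536; power 0.9339. The plan says close to 100%; the chance of missing the effect is 1 − 0.9339 = 6.6%.

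Simulation with 200,000 runs gives 0.549 and 0.934.

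**Step 2: could another reading give the stated pair of figures?**

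| Variant | dz 0.30 | dz 0.50 |
|---|---|---|
| Normal approximation, n = 50 | 56.4% | 94.2% |
| One-sided t, n = 50 | 67.3% | 96.7% |
| One-sided t, n = 40 | 58.7% | 92.8% |
| Two-sided t, n = 60 (no drop-out) | 62.8% | 96.8% |
| Wilcoxon signed-rank (relative efficiency 0.955), n = 50 | 52.8% | 92.3% |

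None gives both. With the stated test, 60% at dz 0.30 needs 57 pairs (0.6049; 56 give 0.5971). That allows (60 − 57)/60 = 5% drop-out, against the 20% assumed. Power of 99% at dz 0.50 needs 76 pairs, more than the whole enrolment.

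**Step 3: the drop-out allowance.**

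- The plan's route: 50 × 1.2 = 60.
- 20% drop-out from 60: 60 × 0.8 = 48. Ten lost from 60 is 10/60 = 16.7%.
- To keep 50: 50/0.8 = 62.5, so 63 enrolled.

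The loss bears on the primary variable. Section 16.7 schedules liver MRI only at baseline and end of study, and the early-withdrawal list in section 16.4 does not name MRI.

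**Step 4: power at n = 48.** df = 47, critical value 2.0117.

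- dz 0.30: λ = 0.30 × √48 = 2.078; power 0.5303, a loss of 0.5477 − 0.5303 = 1.7 points.
- dz 0.50: λ = 0.50 × √48 = 3.464; power 0.9240, a loss of 0.9339 − 0.9240 = 1.0 point. The chance of missing the effect is 7.6%.

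**Step 5: where is power sufficient?** The plan sets no target, so I take the conventional 80% as an assumption. The smallest dz is then 0.404 with 50 pairs and 0.413 with 48. At dz 0.41 and n = 48, power is 0.7945. Reaching 80% at dz 0.30 would take 90 pairs.

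**The case against.** The best reply is that the figures are hedged and may have been read off a power curve, so gaps of 5 to 7 points are loose rounding rather than error. The curve itself did not survive in the text available. The hedge has some force at dz 0.30. It has less at dz 0.50, where 93.4% is described as close to certainty, and both figures err in the favourable direction.

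On drop-out, if the 20% means ten losses per 50 evaluable patients, 60 leaves exactly 50. That is not the usual meaning of a drop-out rate, and the difference is two patients and under 2 points of power. Stopping treatment also does not always mean a missing second scan. Section 15.2 asks for a visit with the relevant assessments where possible, section 15.1 keeps patients whose treatment is suspended for low ferritin in the study, and the per-protocol set keeps those who withdraw for unsatisfactory effect. So 48 assumes that every drop-out lacks an end-of-study MRI. The plan's own allowance makes the same assumption, since it adds patients precisely to replace lost ones.

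The 80% benchmark comes from outside the plan, and section 20.2 does disclose power below 60% at dz 0.30. That disclosure contradicts the sufficiency sentence rather than rescuing it: the sentence fails even if the plan's own power figures and 50 evaluable patients are accepted.

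**Conclusion.** The point holds. For the stated test, power with 50 pairs is 54.8% and 93.4%. With the 48 pairs that the plan's drop-out rate implies, it is 53.0% and 92.4%. The drop-out slip alone is minor. The overstated power and, above all, the claim of sufficient power across 0.3 to 0.5 should be corrected, because the lower part of that range is not adequately powered on any usual standard.

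The power figures follow from the plan's own settings. The figure of 48 assumes that the 20% applies to patients enrolled and that drop-outs have no second MRI. The threshold of about 0.41 assumes an 80% target.

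Power at dz 0.50 stays above 92%, so the arithmetic alone gives no reason to change the enrolment. This says nothing about whether dz 0.50 is a realistic effect, or whether a test of difference suits an endpoint defined by bands of ±1.5 mg/g and ±20%.

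**What to change.** - **Synopsis (Statistical considerations) and section 20.2:** replace the power sentences with: 60 enrolled with an assumed 20% drop-out gives 48 evaluable patients; for a two-sided paired t test at alpha 0.05, power is 53% at dz 0.30, about 80% at dz 0.41 and 92% at dz 0.50.
- **Same two places:** delete the sentence claiming sufficient power from 0.3 to 0.5, or limit it to dz of about 0.41 and above and name 80% as the target.
- **Synopsis (Number of patients), sections 11.2 and 20.3:** replace the 50 + 10 wording with 60 enrolled and 48 expected to be evaluable. A full power statement is not strictly needed here.

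Keep the 20% assumption, which section 11.2 bases on earlier studies. If the sponsor prefers to keep 50 evaluable patients, the matching enrolment is 63, for a gain of 1.7 and 1.0 points; the arithmetic does not require it.

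The cost is wording in five places and slightly less favourable figures. Enrolment, endpoint, analysis sets and test stay as they are.

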15. REMOVAL OF SUBJECTS FROM TREATMENT AND/OR STUDY

15.1. Discontinuation from study treatment

Patients may voluntarily discontinue from the study treatment for any reason at any time.

If a patient decides to discontinue from the study treatment, the investigator should make a reasonable effort (e.g. telephone, e-mail, letter) to understand the reason for this decision and record this information in the patient's chart and on the appropriate CRF pages.

Patients may be considered withdrawn if they state an intention to withdraw, fail to return for visits / lost to follow-up for any other reason.

The investigator should discontinue study treatment for a given patient if, he/she believes that continuation would be detrimental to the patient's well-being.

Study treatment must be discontinued under the following circumstances:

- Death
- Adverse Events
- Abnormal laboratory value
- Pregnancy
- Unsatisfactory therapeutic effect
 - patients with evident inadequate chelation (Transfusion burden > 4 units/month over a three consecutive months period and > 1 PRBC unit/week and a total number of PRBC received >20) the protocol will be discontinued and the patient will be treated as clinically (by label) indicated
- Unwillingness to comply with study procedures/treatment as per protocol
- Discovery of patient ineligibility
- Intake of prohibited medications
- Protocol violation
- Consent withdrawal
- Lost to follow-up
- Administrative problems
- Premature termination of the study
- In patients with serum ferritin <300 ng/ml therapy will be suspended and the patient will remains in study, with the same transfusion (minimal Hb level 9 g/dl) and study criteria. Patients will restart treatment as soon as serum ferritin arise >300 ng/ml.

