16.3. EOT phase

- Physical Examination;
- ECOG;
- Vital Signs;
- Clinical Laboratory Evaluations (see schedule of assessments);
- 12 lead electrocardiograms;
- Echocardiogram
- bone marrow aspirate (if clinically indicated)
- Peripheral blood immunophenotyping in case of suspicious leukemic dissemination;

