16.7. Schedule of blood samples assessments for experimental biological study

		Baseline	Month 1	M 2	M 3	M 4	M 5	M 6	M 7	M 8	M 9	M 10	M 11	EOS
Liver and pancreas MRI (MRI done locally and sent for hepatic and pancreatic iron determination). See Appendix I	Centralized	X												X
NTBI	Centralized	X	X	X	X			X			X			X
LPI	Centralized	X	X	X	X			X			X			X
Epcidine; sTR	Centralized	X			X			X			X			X
Erythroferrone, GDF15, GDF11	Centralized	X			X			X			X			X
MDA Membrane lipid peroxidation	Centralized	X	X	X	X			X			X			X
NGS study	Centralized	X												X

NGS study (molecular tumor analysis) to be performed in case of disease progression

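### No second liver MRI is scheduled for patients stopped early for inadequate chelation, and there is no missing-LIC rule, so the primary comparison may lose patients whom the per-protocol set expressly keeps

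*Combined protocol and SAP*

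**What the plan says.** **Who is analysed.** Section 20.3 defines the full analysis set (FAS) as everyone enrolled. The per-protocol (PP) set is treated patients "without any major protocol violations and complete the treatment study phase or withdraw from the study due to unsatisfactory therapeutic effect". Efficacy parameters are to be analysed on both sets.

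**What is measured.** The primary variable (17.2.1, 20.3) is the change in LIC by R2-MRI from baseline to end of study. It is read against bands of ±1.5 mg/g dw for baseline LIC up to 5, and ±20% above that. Section 20.3 analyses the difference as a continuous variable.

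**When it is measured.** The synopsis lists the MRI liver scan as "YES Baseline and EOS", quantity 2. In section 16.7 the row "Liver and pancreas MRI (MRI done locally and sent for hepatic and pancreatic iron determination" is marked only at Baseline and EOS, and the table has no early-withdrawal column.

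**Who stops.** Under unsatisfactory effect, section 15.1 names "patients with evident inadequate chelation (Transfusion burden > 4 units/month over a three consecutive months period", together with two further conditions on weekly and total units. For these patients "the protocol will be discontinued and the patient will be treated as clinically (by label) indicated". For low ferritin, by contrast, "therapy will be suspended and the patient will remains in study".

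**What happens at exit.** The early-withdrawal list in 16.4 names no MRI. Its nearest item is "Any test needed if withdrawal is for toxic reason". Section 15.2 asks a patient who withdraws to return, when possible, for whichever assessments are relevant, and does not name MRI.

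**The concern.** A change score needs two LIC values. The PP definition deliberately keeps patients who leave for unsatisfactory effect, yet the schedule gives them no second scan when they leave, and the analysis section does not say what to do without one. It also does not say what to do with a scan taken after by-label chelation has begun, when the value reflects a different treatment.

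This is an uncontrolled trial whose claim is iron balance over one year. The stop for inadequate chelation is triggered by heavy transfusion, which is the source of the iron being measured. Missing values in this group are therefore plausibly related to the outcome, and a comparison of completers alone could look more balanced than the treated population was. The 10 extra patients planned for drop-out restore numbers. They do not correct a selective loss, and a scan not taken at exit cannot be recovered later.

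**Working it through.** The plan gives no figure for the number of such stops or for their LIC change, so there is nothing of its own to reproduce. The check is first textual, then illustrative.

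**1. Follow one patient stopped at month 6 for inadequate chelation.** As written, a site could:
- scan at exit: the change covers 6 months, and no rule says how it is pooled with 12-month changes;
- scan at month 12: the value follows by-label chelation, and no rule covers it;
- not scan: there is no change score, and no rule covers that either.

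The patient belongs to the FAS in every case, and to PP if there is no major violation.

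**2. Possible size of the rise in such a patient.**
- From the documents: more than 4 units/month for 3 months (15.1); under 2 units/month at entry (synopsis); body iron in mg/kg = 10.6 × LIC, standard error 7.3 (8.2); the 1.5 band; 50 + 10 patients (11.2).
- Assumed: 200 mg iron per unit (180 to 250), body weight 70 kg (80 to 60), chelation removing 25%, 50% or 75%, and k patients lost.

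Three qualifying months mean more than 3 × 4 = 12 units, against fewer than 6 at the entry ceiling.
- Gross rise: 12 × 200 / 70 = 34.3 mg/kg; 34.3 / 10.6 = 3.2 mg/g dw.
- Low: 12 × 180 / 80 / 10.6 = 2.5. High: 12 × 250 / 60 / 10.6 = 4.7.
- If the 7.3 is read as mg/kg, it adds ±7.3 / 10.6 = ±0.7. The factor itself comes from thalassemia.
- Net after 25%, 50% or 75% removal: 2.4, 1.6 or 0.8 mg/g dw.

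**3. Shift in the mean.** With 50 analysed at mean m and k lost at mean D, the mean over all patients minus the completers' mean is k(D − m)/(50 + k). With m set to 0:

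| D (mg/g dw) | k = 1 | k = 3 | k = 5 |
|---|---|---|---|
| 0.8 | 0.02 | 0.05 | 0.07 |
| 1.6 | 0.03 | 0.09 | 0.15 |
| 2.4 | 0.05 | 0.14 | 0.22 |

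Harsher assumptions, with 5% to 20% of patients lost and a mean gain of 2 to 5 mg/g dw, give 0.05 × 2 = 0.10 up to 0.20 × 5 = 1.0.

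**4. Is the sign fixed?** No. It depends on D − m, and m = 0 was assumed. On the same inputs a completer at 1 unit/month also receives 12 units in the year (3.2 gross). One just under 2 units/month receives almost 24: 24 × 200 / 70 / 10.6 = 6.5 gross. Completers' gross loading can therefore match or exceed that of the three qualifying months. If completers lose iron on average (m below 0), leaving out patients with D above 0 can move the mean away from zero.

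**5. If the bands are used.** Counting k lost patients as not balanced multiplies the completers' proportion by 50/(50 + k): 0.98, 0.94 or 0.91 for k = 1, 3 or 5. It is 50/60 = 0.83 if all 10 planned drop-outs lack a second LIC and are counted that way.

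**6. Why the exit LIC alone should not decide band status.** A rise equivalent to 1.5 per year is 1.5 × 3/12 = 0.38 at month 3, 0.75 at month 6 and 1.13 at month 9. A patient who rises 1.4 by month 3 sits inside the 1.5 band, although 1.4 × 12/3 = 5.6 per year. Annualising multiplies measurement error by the same factor: 4 at month 3, 2 at month 6.

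**The case against.** **Section 15.2 provides for a return visit** and keeps data already collected, including central-review data; liver iron is determined centrally. This is the nearest counter-text, and it could lead some sites to scan. But it applies when possible, does not name MRI, and gives no analysis rule. It supports saying that patients *may* be lost rather than *will* be.

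**The omission in 16.4 is weak evidence alone.** That stands. The end-of-treatment list in 16.3 also omits MRI and refers outward ("Clinical Laboratory Evaluations (see schedule of assessments"), and 16.5 sends the reader to the schedule for experimental tests. The point rests on that schedule, 16.7, which is silent about early stops.

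**A reader might infer that EOS is undefined.** For completers it is not: EOS is the column after month 11 and treatment lasts 12 months. The mixed use of EOS and EOT in 20.3 is loose wording. Only early stops are left without a defined end value.

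**A reader might infer that the set for the primary variable is unclear.** The documents do not support that. Section 17.2 is headed efficacy parameters and opens with the primary endpoint, and 20.3 assigns efficacy parameters to FAS and PP. The Efficacy Population in 17.1 is a separate editorial matter.

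**The PP wording is not emptied by the MRI schedule.** That also stands: the sets serve ferritin, transferrin saturation, NTBI and LPI as well, which are measured repeatedly during follow-up.

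**Conclusion.** The gap is real and sits in the primary endpoint. Followed as written, the plan can leave patients whom PP expressly keeps, and other early stops in the FAS, without a usable LIC change, and no rule says what happens then.

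Two stronger readings are tempting. The first is that the loss always pushes the result towards balance. Steps 3 and 4 show that this sign follows from setting the completers' mean to zero with a positive rise in those lost. The second is that the loss is one-sided because low-ferritin patients stay in study while the inadequately chelated leave. Section 15.1 also lists adverse events, abnormal laboratory values, death, consent withdrawal and loss to follow-up. Those patients may equally lack a second scan, and their direction is unknown.

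What can be said is that loss through the inadequate-chelation stop is plausibly informative and could favour apparent balance. Its size is unknown and may be small: the stop joins three conditions, and the transfusion rate must more than double from the entry ceiling. The illustrative shift of 0.02 to 0.22 mg/g dw is at most about 15% of the 1.5 band (0.22/1.5). The figure of 1.0 requires a fifth of patients lost with a 5 mg/g dw gain. All these sizes rest on assumed iron per unit, weight, removal fraction and number lost, or on assumed loss rates and gains. The case for change is that the gap should be fixed because it is cheap to close in advance and cannot be repaired afterwards, not that a large bias has been shown.

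**What to change.** 1. **Sections 16.4 and 16.7.** Bring the planned second liver MRI forward to the early-discontinuation visit where feasible and without delaying care. Record its date and whether by-label chelation had begun. The total stays at two scans per patient.
2. **Section 20.3, bands.** When the ±1.5 mg/g dw or ±20% bands are applied, count withdrawals for unsatisfactory effect as not balanced in the main FAS and PP analyses, whatever the exit LIC.
3. **Section 20.3, continuous change.** Include the exit LIC and report its interval. Show results with and without exit and post-switch values, and for completers only.
4. **Reporting.** Give the number of patients without a second LIC by reason for stopping, and use one term for EOS/EOT.

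The stopping rule is not changed. The cost is one line in 16.4, one column or footnote in 16.7 and one paragraph in 20.3. The downside is that some LIC values will cover less than 12 months, so intervals become unequal, and the balanced proportion may come out slightly lower.
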